#### **4.4.4 Sensitivity Analyses**

The analysis of primary efficacy endpoint described in Section 4.4.1 will be performed for the PP population as a sensitivity analysis. Per study schedule, the last EDSS assessment is at Week 96, such that no subsequent visit with EDSS measurement can be used to confirm an initial disability progression at Week 96. A Sensitivity analysis will be performed for the mITT population to impute 50% of the patients with an initial disability progression at Week 96 as having an event of CDP; the other 50% of these patients as having no event of CDP.

#### **4.4.5 Subgroup Analyses**

The primary and all secondary outcomes will be analyzed for the following subgroup for the mITT population:

Last DMT before enrollment: Fingolimod vs. Other

### **4.5 PHARMACOKINETIC AND PHARMACODYNAMIC ANALYSES**

Not Applicable.

### **4.6 PATIENT REPORTED OUTCOME ANALYSES**

All analyses on the patient reported outcomes (PROs) will be based on the ITT population.

#### **4.6.1 MSIS-29**

The Multiple Sclerosis Impact Scale (MSIS-29) is a 29-item questionnaire designed to measure the physical and psychological impact of MS from the patient's perspective.

| Dimension           | Items | Item Scores   |
|---------------------|-------|---|
| Physical Scale      | 1-20  | 1 = Not at all
2 = A little
3 = Moderately
4 = Extremely |
| Psychological Scale | 21-29 | 1 = Not at all
2 = A little                                    |

|  |  |                |
|--|--|----------------|
|  |  | 3 = Moderately |
|  |  | 4 = Extremely  |

Score for the physical scale is calculated as follows:

- Items 1-20 are added
- A transformed score =  $100 \times (\text{observed score} - 20) / (80-20)$  is derived

Score for the psychological scale is calculated as follows:

- Items 21-29 are added
- A transformed score =  $100 \times (\text{observed score} - 9) / (36-9)$  is derived

Higher scale values indicate higher impact of MS disability on the patient. Missing scores in the specific scale are not imputed.

MSIS-29 results by dimension will be summarized for baseline and weeks 24, 48, 72, and 96 visits. The mean change in each MSIS-29 dimension score from baseline to weeks 24, 48, and 96 will be analyzed using a longitudinal mixed effects model repeated measure (MMRM). The fixed effects will include visit along with the following baseline covariates: baseline MSIS-29 score, number of previous DMTs (1 vs >1), baseline MSIS-29 score by visit interaction, and baseline EDSS score (< 2.5 vs.  $\geq 2.5$ ). Visit will be treated as a repeated variable within a patient. Patient and visit will be treated as factor variables. An unstructured variance-covariance structure will be applied to model the within-patient errors. The model will be fitted using the Restricted Maximum Likelihood method (REML). Denominator degrees of freedom will be estimated using Satterthwaite's approximation.

A plot of the least squares mean changes from baseline in MSIS-29 scores over time and the corresponding 95% confidence intervals will be presented for each dimension of the scale.

#### **4.6.2 SATMED-q**

The Treatment Satisfaction with Medicines Questionnaire includes 17 questions scored on a 5-point Likert-type scale investigating the following dimensions. The bolded dimensions will be summarized:

| Dimension                       | Items | Item Scores  |
|---------------------------------|-------|--|
| Any Undesirable side effects    | 1     | 0=No
1=Yes                                      |
| Undesirable Side effects | 1-3   | 4 = Not at all
3 = A little bit
2 = Somewhat |

|                                   |       |  |
|-----------------------------------|-------|--|
|                                   |       | 1 = Quite a bit
0 = Very much   |
| Treatment effectiveness    | 4-6   | 0 = Not at all
1 = A little bit
2 = Somewhat
3 = Quite a bit
4 = Very much |
| Convenience for use        | 7-9   | 0 = Not at all
1 = A little bit
2 = Somewhat
3 = Quite a bit
4 = Very much |
| Impact on daily activities | 10-12 | 0 = Not at all
1 = A little bit
2 = Somewhat
3 = Quite a bit
4 = Very much |
| Medical care                      | 13-14 | 0 = Not at all
1 = A little bit
2 = Somewhat
3 = Quite a bit
4 = Very much |
| Global satisfaction               | 15-17 | 0 = Not at all
1 = A little bit
2 = Somewhat
3 = Quite a bit
4 = Very much |

Items are summed to yield the dimension scores. Higher scores indicate higher satisfaction with treatment. Missing score should be substituted by the worst possible score where applicable (items 1 to 3: if question “Have you experienced any undesired effects caused by the medicine” = “Y”, then missing=“Quite a bit”, otherwise missing will not be imputed; items 4 to 17: missing=“Not at all”). If two or more answers are missing in a given dimension, the dimension should be discarded. If two contiguous response categories are selected for one item, the worst score should be selected as valid. When two non-contiguous response categories are selected, the response should be considered as missing.

Analysis of the SATMED-q scores will be based on a longitudinal MMRM similar to the planned analyses of the MSIS-29 scores as described above.

A plot of the least squares mean changes from baseline in SATMED-q scores over time and the corresponding 95% confidence intervals will be presented for each bolded dimension of the scale.

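### SAP 4.6.2 gives missing SATMED-q side-effect items 1-3 the second-worst code, although the same paragraph requires the worst (minor; exploratory PRO only)

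*SAP*

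**What the plan says.** SAP Section 4.6.2 sums SATMED-q items into dimension scores and fixes the direction: "Higher scores indicate higher satisfaction with treatment". The general rule for a missing item is "Missing score should be substituted by the worst possible score where applicable".

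A parenthesis then applies the rule. For items 1-3, if the patient answered yes to having had undesired effects, a missing item becomes *Quite a bit*. The parenthesis goes on: "otherwise missing will not be imputed; items 4 to 17" take *Not at all*. In the scoring table, the bottom of the scale for items 1-3 reads "1 = Quite a bit 0 = Very much"; for items 4-17 the bottom code is *Not at all* = 0.

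Three further rules matter here:

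- Adjacent double marks: "If two contiguous response categories are selected for one item, the worst score should be selected as valid".
- Non-adjacent double marks: "When two non-contiguous response categories are selected, the response should be considered as missing".
- Discarding: "If two or more answers are missing in a given dimension, the dimension should be discarded".

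The SAP adds "The bolded dimensions will be summarized". Undesirable Side effects (items 1-3) is one of these, so it is modelled by MMRM and plotted. SAP Sections 2.2.3 and 4.4.3 class the patient-reported outcomes as exploratory.

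**The concern.** The paragraph states a principle and then gives a value that breaks it. A programmer who follows the principle codes 0; one who follows the parenthesis codes 1. The result is also out of order within the item: an adjacent double mark on the two worst categories scores lower than a blank.

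At stake is the SATMED-q side-effects dimension and its change from baseline. Under Protocol Section 4.5.9 the baseline questionnaires refer to the last-used DMT and later ones to ocrelizumab. The share of patients who report side effects and leave one item blank may therefore differ between baseline and later visits, so the discrepancy need not cancel in the change score. The primary endpoint, the secondary endpoints, the adverse-event analyses and the MSIS-29 do not use this rule.

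**Working it through.** **Inputs, all from SAP 4.6.2 unless stated**

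| Items | Codes from best to worst | Imputed category | Imputed code | Lowest code |
|---|---|---|---|---|
| SATMED-q 1-3 (side effects = yes) | 4, 3, 2, 1, 0 | *Quite a bit* | 1 | 0 (*Very much*) |
| SATMED-q 4-17 | 4, 3, 2, 1, 0 | *Not at all* | 0 | 0 (*Not at all*) |
| TSQM II side-effect items 4-6 (side effects = yes; SAP 4.6.3) | 5, 4, 3, 2, 1 | *Extremely Dissatisfied* | 1 | 1 (*Extremely Dissatisfied*) |

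**Step 1: is the imputed value the worst score?** Higher is better, so worst = min{4, 3, 2, 1, 0} = 0, which is *Very much*. The imputed code 1 is second from the bottom. Reversing the direction does not help, because the extreme would then be *Not at all* (4). The SAP's value is not reproduced as the worst score under either direction.

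**Step 2: do the neighbouring rules behave the same way?** No. The second and third rows of the table both impute their own minimum. Only items 1-3 depart from it.

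**Step 3: consistency within an item, for a patient who reports side effects**

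- *Quite a bit* and *Very much* both marked: adjacent, so the worse score applies, giving 0.
- Item left blank: imputed, giving 1.
- *Somewhat* and *Very much* both marked: not adjacent, so treated as missing and imputed, giving 1.

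**Step 4: size per patient.** The dimension is a sum of three items coded 0 to 4, so its range is 0 to 3 × 4 = 12. With missing answers counted for the discard rule before imputation, two or more missing answers discard the dimension, so at most one item is imputed. The difference is 1 − 0 = 1 point, and 1/12 = 8.3% of the range.

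**Step 5: size for a visit mean.** Let m be the share of scored patients at a visit who have one imputed item. The shift is m × 1 point. The documents give no value for m, so these are assumptions:

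| m (assumed) | Shift in visit mean | Share of the 12-point range |
|---|---|---|
| 1% | 0.01 | 0.08% |
| 5% | 0.05 | 0.42% |
| 10% | 0.10 | 0.83% |

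**Step 6: size for mean change from baseline.** The shift is (m at the visit − m at baseline) × 1 point. It is zero if the two shares are equal and can take either sign.

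**The case against.** **The specific instruction may be the intended one.** The principle and the instruction conflict, and the documents do not show which should yield. Neither reference list contains a SATMED-q scoring source. This stands in part: it leaves the sponsor a second way to resolve the conflict, but either way the paragraph needs an edit. The words *where applicable* do not resolve it. They limit when imputation happens (only after a yes); they do not change the value.

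**Too high compared with what?** A reader might infer that the rule inflates satisfaction above what patients really felt. The documents do not support that, because a code of 1 is already pessimistic and the true answer is unknown. The 1-point excess is relative to the SAP's stated rule only.

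**It is small.** That stands. The endpoint is exploratory in a single-arm, mostly descriptive study (Protocol Section 6), and the shifts in the mean are fractions of a point.

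**Stronger readings that the text does not bear out.** A reader might infer that SAP 4.6.3 allows two TSQM II Side Effects scores from the same answers, because the table prints its formula for one missing item without a condition. But the text below the table imputes all missing or not-applicable side-effect items after a yes, and none otherwise. The formula therefore has work to do only for the other patients.

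A reader might also infer that the discard rule is defeated, because neither section says whether missing answers are counted before or after imputation. Counting afterwards would leave the SATMED-q rule with nothing to act on for items 4-17, so counting first is the order that keeps it working. SAP Appendix 3 also places further data-handling rules in DAP Module 2, which was not supplied and may state both points.

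**Conclusion.** The point holds as a minor scoring error in an exploratory analysis. For patients who report side effects, SAP 4.6.2 fills a missing SATMED-q item 1-3 with the second-worst code while requiring the worst. An affected Undesirable Side effects score is 1 of 12 points (8.3%) above what the SAP's own rule gives. This assumes one imputed item, which follows if missing answers are counted before imputation. The visit-mean shift of 0.01 to 0.10 points rests on assumed shares of 1% to 10%.

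The contradiction is visible within SAP 4.6.2 alone, so an unseen programming document could not make that paragraph consistent. The scope of the TSQM II formula and the order of counting are details worth stating, not errors.

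**What to change.** In SAP 4.6.2, change the category imputed for items 1-3 from *Quite a bit* to *Very much* (0), which matches the stated principle and the neighbouring rules. If the sponsor intends *Quite a bit* because the instrument's scoring manual says so, it should instead remove the worst-score wording for these items and cite the manual.

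Optional clarifications: in 4.6.3, say that the one-missing Side Effects formula applies only where items are not imputed. In both sections, say that missing answers are counted for the discard rule before any imputation. If DAP Module 2 already covers these, a cross-reference is enough.

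The cost is one category label (or one reworded sentence with a citation) and the matching line of scoring code, plus a sentence or two per section for the clarifications. No new data and no new analysis are needed.

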#### **4.6.3 TSQM II**

The Treatment Satisfaction Questionnaire for Medication Version II consists of 11 questions and 4 dimensions

| Dimension | Cluster of | Score | Scoring |
|-----------|------------|-------|---------|
|-----------|------------|-------|---------|

**Ocrelizumab—Genentech, Inc.**  
26/Statistical Analysis Plan MN30035

| Items that are added |       |  |  |
|----------------------|-------|--|--|
| Effectiveness        | 1-2   | 1 = Extremely Dissatisfied
2 = Very Dissatisfied
3 = Dissatisfied
4 = Somewhat Satisfied
5 = Satisfied
6 = Very Satisfied
7 = Extremely Satisfied  | $([(item\ 1 + item\ 2) - 2]/12) * 100$

If one item is missing:
$([(Use\ the\ completed\ item)) - 1] / 6) * 100$                            |
| Side Effects         | 4-6   | 1 = Extremely Dissatisfied
2 = Very Dissatisfied
3 = Somewhat Dissatisfied
4 = Slightly Dissatisfied
5 = Not at all Dissatisfied
(6) = Not Applicable | $([Sum(item\ 4 - item\ 6) - 3] / 12) * 100$

If one item is missing:
$([Sum(the\ two\ completed\ items)) - 2]/8) * 100$                     |
| Convenience          | 7-9   | 1 = Extremely Dissatisfied
2 = Very Dissatisfied
3 = Dissatisfied
4 = Somewhat Satisfied
5 = Satisfied
6 = Very Satisfied
7 = Extremely Satisfied  | $([Sum(item\ 7 - item\ 9) - 3]/18) * 100$

If one item is missing:
$([Sum(the\ two\ completed\ items)) - 2]/12) * 100$                      |
| Global Satisfaction  | 10-11 | 1 = Extremely Dissatisfied
2 = Very Dissatisfied
3 = Dissatisfied
4 = Somewhat Satisfied
5 = Satisfied
6 = Very Satisfied
7 = Extremely Satisfied  | $([Sum(item\ 10\ to\ Item\ 11) - 2] / 12) * 100$

If one item is missing:
$([(Use\ the\ completed\ item)) - 1] \text{ divide by } 6) * 100$ |

All missing or 'not applicable' responses for Side Effects (relevant to item 4 – item 6) will be imputed as "Extremely Dissatisfied" if the question "As a result of taking this medication, do you experience any side effects at all?" is answered as "Yes"; otherwise will not be imputed. If two or more item is missing in a subscale, the subscale will be discarded.

Analysis of the TSQM II scores will follow the MMRM approach similar to the analysis of the MSIS-29 scores as described above.

A plot of the least squares mean changes from baseline in TSQM-II scores over time and the corresponding 95% confidence intervals will be presented for each of the four dimension scales.

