### **2.2.3 Exploratory Efficacy Outcome Measures**

- Change in neurological exam score (EDSS) at Weeks 24, 48 and 96 from baseline
- Percent change in brain volume at Weeks 24, 48, and 96 from baseline
- Change in Patients Reported Outcome Scales from baseline:
  - MSIS-29 - The Multiple Sclerosis Impact Scale
  - SATMED-q - The Treatment Satisfaction with Medicines Questionnaire
  - TSQM II - The Treatment Satisfaction Questionnaire for Medication Version II

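### The SAP gives no side-effect score on TSQM II (and on SATMED-q, if the items are skipped) to a patient who reports no side effects and leaves the items blank or not applicable

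*SAP*

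**What the plan says.** Both instruments include a yes/no question on side effects and three items on how much those effects matter.

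- **TSQM II (SAP 4.6.3).** Items 4-6 run from 1 (worst) to 5 (best), with a further option for patients to whom the item does not apply: "5 = Not at all Dissatisfied (6) = Not Applicable". The imputation rule treats two kinds of response alike: "All missing or 'not applicable' responses for Side Effects". Both become the worst score if the side-effect question is answered Yes. In all other cases the item "otherwise will not be imputed. If two or more item is missing in a subscale, the subscale will be discarded".
- **SATMED-q (SAP 4.6.2).** Items 1-3 are reverse scored, so the best answer earns most: "4 = Not at all 3 = A little bit 2 = Somewhat". A missing item is filled with an unfavourable value if side effects were reported; "otherwise missing will not be imputed; items 4 to 17" follow a separate rule. Then: "If two or more answers are missing in a given dimension, the dimension should be discarded". No not-applicable option is listed.

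The endpoint is exploratory (SAP 2.2.3): "Change in Patients Reported Outcome Scales from baseline". It is analysed in the ITT population by an MMRM for Weeks 24, 48 and 96 with the baseline score as a covariate (SAP 4.4.3, 4.6 and 4.6.1). Protocol 4.5.9 ties the baseline questionnaires to the last DMT used before enrolment, so the change compares the old drug with ocrelizumab.

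**The concern.** On both scales a higher score means greater satisfaction, and having no side effects is the best state a patient can report. The SAP supplies a value when side effects are present and an item is blank. It supplies none when side effects are absent and the items are blank or not applicable.

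Whether a score exists then depends on the quantity being measured. A patient whose side effects end after the switch loses the follow-up scores at the visits without them. A patient who had none on the prior DMT has no baseline score and cannot enter the model, so any new side effects on ocrelizumab are not counted. The first loss hides improvement and the second hides worsening. An MMRM is valid under missing at random given the observed data. Here it would predict the unscored visits from patients who still have side effects, so it does not correct the problem.

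At stake is whether the plotted mean changes on these two scales describe the ITT population or an unreported selection from it.

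**Working it through.** **1. The scoring formula.** TSQM II Side Effects is (sum of items 4-6 − 3)/12 × 100, or (sum of two items − 2)/8 × 100 when one is missing.

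- Items 1,1,1: (3 − 3)/12 × 100 = 0. Items 5,5,5: (15 − 3)/12 × 100 = 100.
- Two items 1,1: (2 − 2)/8 × 100 = 0. Two items 5,5: (10 − 2)/8 × 100 = 100.

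The SAP's divisors are right and the scale runs from 0 to 100.

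**2. The rules applied to response patterns.** Not applicable is treated as missing, and imputation is assumed to precede discarding (the SAP does not state the order).

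| Side-effect question | Items | TSQM II | SATMED-q |
|---|---|---|---|
| No | all three blank (or N/A, TSQM II) | no score | no score |
| No | one best answer, two missing | no score | no score |
| No | two best answers, one missing | 100 | 8 if simply summed |
| No | three best answers | 100 | 12 |
| Yes | all three blank | 0 | 3 |

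The score is lost through missing or not-applicable items. The answer No does not by itself remove it.

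**3. Other rules that might catch it.** SAP 4.8 covers adverse-event attributes and dates. The sensitivity analyses in SAP 4.4.4 concern the primary endpoint. The SATMED-q yes/no item is in the table but is not among the dimensions marked for summary, and the TSQM II yes/no question has no scale of its own.

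**4. How many might be scored.** Let a be the share with side effects on the prior DMT and b the share on ocrelizumab at one visit. Suppose every unaffected patient is unscored. The number scored at both times is 600ab under independence, with bounds 600 × max(0, a + b − 1) and 600 × min(a, b).

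The documents give neither a nor b. As rough stand-ins, Protocol 1.2.1.2 reports 34.3% with infusion-related reactions on ocrelizumab and 83.3% with any adverse event in both groups of the pooled Phase III relapsing MS studies. The 30% and 50% are assumptions.

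| a | b | Independent | Bounds |
|---|---|---|---|
| 0.30 | 0.343 | 62 (10%) | 0 to 180 |
| 0.50 | 0.343 | 103 (17%) | 0 to 206 |
| 0.50 | 0.833 | 250 (42%) | 200 to 300 |
| 0.833 | 0.833 | 416 (69%) | 400 to 500 |

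These are single-visit counts. The number contributing to the MMRM is larger, because a patient with a baseline score needs only one scored visit among Weeks 24, 48 and 96.

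**5. Direction of bias (illustration).** Assume a mean TSQM II score m among affected patients at both times, and 100 for unaffected patients. The as-written change is then 0 by construction. With unaffected patients scored, the change is (a − b)(100 − m). At m = 60:

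- a = 0.70, b = 0.343: 0.357 × 40 = +14.3
- a = 0.50, b = 0.343: 0.157 × 40 = +6.3
- a = b: 0
- a = 0.343, b = 0.50: −0.157 × 40 = −6.3
- a = 0.50, b = 0.833: −0.333 × 40 = −13.3

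Across these pairs the extremes are +17.9 and −16.6 at m = 50, and +8.9 and −8.3 at m = 75.

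**The case against.** The SAP does not say that patients answering No skip the items. Both scales have a best response, and a patient who ticks it three times gets the maximum, 100 or 12. SATMED-q lists no not-applicable option, so there the loss depends on a form that is not in the documents. This stands, and it makes the SATMED-q half of the point conditional. For TSQM II the case is firmer: a not-applicable option exists and is handled as missing.

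Three stronger readings are tempting but not supported:

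- **Every patient without side effects is dropped.** Only those with two or more items missing or not applicable are.
- **Only patients with side effects both before and on ocrelizumab contribute.** Even under full skipping, the model needs a baseline score and one analysed post-baseline score. A patient free of side effects at some visits stays in through the others.
- **Code 6 could enter the sum and give (18 − 3)/12 × 100 = 125.** The option "6) = Not Applicable" has its code in parentheses, and the imputation rule groups it with missing responses. The natural reading is a missing code.

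It is also fair to say that satisfaction among patients who have side effects is a coherent quantity, and that scoring No as best defines a different one. But the SAP does not state that restricted quantity, and the change analysis is presented for the ITT population. SAP Appendix 3 refers to further data-handling rules in DAP Module 2, which is not available here; a best-score rule there would contradict the SAP's own statement that these items are not imputed.

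Finally, this touches two of ten summarised PRO scales (two MSIS-29, four SATMED-q, four TSQM II), all exploratory, in a single-arm and mostly descriptive study. Tolerability as the secondary objective is measured by adverse events. That limits the weight of the point but does not supply the missing rule.

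**Conclusion.** The point holds in conditional form. A TSQM II patient who answers No and leaves two or more of items 4-6 blank or not applicable has no Side Effects score. The same is true of SATMED-q items 1-3 if the form has patients skip them. Where this happens, missingness depends on the outcome and neither the MMRM nor any other rule in the SAP repairs it.

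The size cannot be fixed from the documents. The 10% to 69% range assumes that all unaffected patients are unscored, that side effects before and after the switch are independent, and that the shares lie in the ranges above. The point differences also assume a mean for affected patients that does not change over time. A reader might infer that the plan favours or disfavours ocrelizumab; the calculation supports neither, since the sign follows whichever treatment has more side effects and the difference vanishes when the shares are equal. No primary or secondary efficacy result, adverse-event summary or other PRO scale is affected.

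**What to change.** In SAP 4.6.2 and 4.6.3:

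1. State whether patients answering No are directed past the side-effect items.
2. When the answer is No and the items are blank or not applicable, assign the best score, after checking against the instrument manuals: 5 on each of TSQM II items 4-6 (scale score 100) and 4 on each of SATMED-q items 1-3 (total 12).
3. State that TSQM II code 6 is handled as missing and never summed.
4. Beside the scale means, report the percentage answering Yes and the number scored at each visit.
5. Keep the scoring as now written as a sensitivity analysis.

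This takes a few SAP sentences and a change to the scoring program, and uses data already collected. The small downside is a ceiling effect on both scales, which the reported percentage answering Yes makes visible.
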